#### **6.5 Critical Structures**

6.5.1 Critical Organ Dose-Volume Limits

The following tables lists maximum dose limits to a point or volume within several critical organs. These are absolute limits, and dose that exceeds these limits by 5% will constitute a major protocol violation.

These limits were formulated with the approval of the study committee using known tolerance data, radiobiological conversion models, norms used in current practice at academic centers. Participating centers are encouraged to observe prudent treatment

planning principles in avoiding unnecessary radiation exposure to critical normal structures irrespective of these limits. The tables list limits for previously non-irradiated tissues. Previous radiation dose should be quantified. Clinicians should factor in previous radiation by modifying the actual dose tolerance limits employed in a given patient on a case by case basis.

In order to verify each of these limits, the organs must be contoured such that appropriate dose volume histograms can be generated. Instruction for the contouring of these organs will follow below.

6.5.20ne Fra Serial Tissue	Volume	Volume Max	Max Point Dose	Endpoint (≥Grade 3)
Serial Hissue	,	(Gy)	(Gy)	Enupoint (201 aut 5)
Brainstem	<1 cc	10 Gy	15 Gy	cranial neuropathy
Spinal Cord	See section	10 0 9	15 Gy	myelitis
Spinar Cora	6.1.2			
Cauda Equina	<5 cc	14 Gy	16 Gy	neuritis
Esophagus*	<5 cc	14.5 Gy	19 Gy	stenosis/fistula
Ipsilateral Brachial Plexus	<3 cc	14.4 Gy	16 Gy	neuropathy
Heart/Pericard ium	<15 cc	16 Gy	22 Gy	pericarditis
Great vessels	<10 cc	31 Gy	37 Gy	aneurysm
Trachea and Ipsilateral Bronchus*	<4 cc	8.8 Gy	22 Gy	stenosis/fistula
Skin	<10 cc	14.4 Gy	16 Gy	ulceration
Stomach	<10 cc	13 Gy	16 Gy	ulceration/fistula
Duodenum*	<5 cc	8.8 Gy	16 Gy	ulceration
Jejunum/Ileu m*	<5 cc	9.8 Gy	19 Gy	enteritis/obstruction
Colon*	<20cc	11 Gy	22 Gy	colitis/fistula
Renal hilum/vascula r trunk	<2/3 volume	10.6 Gy		malignant hypertension
Parallel Tissue	Critical Volume (cc)	Critical Volume Dose Max (Gy)		Endpoint (≥Grade 3)
Lung (Right & Left)	1500 cc	7 Gy		Basic Lung Function
Lung (Right & Left)	1000 cc	7.4 Gy		Pneumonitis
Liver	700 сс	9.1 Gy		Basic Liver Function
Renal cortex (Right & Left)	200 cc	8.4 Gy		Basic renal function

#### 6.5.2**One Fraction**

Serial Tissue	Volume	Volume Max (Gy)	Max Point Dose (Gy)	Endpoint (≥Grade 3)
Brainstem	<1 cc	26 Gy (5.2 Gy/fx)	31 Gy (6.2 Gy/fx)	cranial neuropathy
Spinal Cord	See section 6.1.2			myelitis
Cauda Equina	<5 cc	30 Gy (6 Gy/fx)	34 Gy (6.4 Gy/fx)	neuritis
Esophagus*	<5 cc	27.5 Gy (5.5 Gy/fx)	35 Gy (7 Gy/fx)	stenosis/fistula
Ipsilateral Brachial Plexus	<3 cc	30 Gy (6 Gy/fx)	32 Gy (6.4 Gy/fx)	neuropathy
Heart/Pericard ium	<15 cc	32 Gy (6.4 Gy/fx)	38 Gy (7.6 Gy/fx)	pericarditis
Great vessels	<10 cc	47 Gy (9.4 Gy/fx)	53 Gy (10.6 Gy/fx)	aneurysm
Trachea and Ipsilateral Bronchus*	<4 cc	18 Gy (3.6 Gy/fx)	38 Gy (7.6 Gy/fx)	stenosis/fistula
Skin	<10 cc	30 Gy (6 Gy/fx)	32 Gy (6.4 Gy/fx)	ulceration
Stomach	<10 cc	28 Gy (5.6 Gy/fx)	32 Gy (6.4 Gy/fx)	ulceration/fistula
Duodenum*	<5 cc	18 Gy (3.6 Gy/fx)	32 Gy (6.4 Gy/fx)	ulceration
Jejunum/Ileu m*	<5 cc	19.5 Gy (3.9 Gy/fx)	35 Gy (7 Gy/fx)	enteritis/obstruction
Colon*	<20cc	25 Gy (5 Gy/fx)	38 Gy (7.6 Gy/fx)	colitis/fistula
Renal hilum/vascula r trunk	<2/3 volume	23 Gy (4.6 Gy/fx)		malignant hypertension
Parallel Tissue	Critical Volume (cc)	Critical Volume Dose Max (Gy)		Endpoint (≥Grade 3)
Lung (Right & Left)	1500 cc	12.5 Gy (2.5 Gy/fx)		Basic Lung Function
Lung (Right & Left)	1000 cc	13.5 Gy (2.7 Gy/fx)		Pneumonitis
Liver	700 сс	21 Gy (4.2 Gy/fx)		Basic Liver Function
Renal cortex	200 cc	17.5 Gy (3.5		Basic renal function

Five Fractions – These limits for non-irradiated tissues. Clinician must account for previous dose to normal structures using clinical judgement on a case by case basis.

(Right & Left) Gy/fx)		
-----------------------	--	--

#### \*Avoid circumferential irradiation

#### **6.6 Contouring of Normal Tissue Structures**

6.6.1 Spinal Cord

The spinal cord will be contoured as multiple structures based on MRI or CT. Ideally the actual spinal cord and not necessarily the entire spinal canal will be contoured if possible. For each treated site, the spinal cord should be contoured on axial slices in the region of the PTV and extending at least 2.5 cm above and below the PTV. Each section of contoured spinal cord will be evaluated separately.

6.6.2 Cauda Equina

The cauda equina will be contoured as multiple structures based on MRI. For each treated site, the cauda equina should be contoured on axial slices if it is within 5 cm of the PTV. The superior aspect of the cauda equina begins at the conus medularis. The entire spinal canal will be contoured to represent the cauda equine extending inferiorly to the end of the thecal sac.

6.6.3 Lungs

Both the right and left lungs should be contoured as one structure. Contours should be carried out using pulmonary windows on CT. Any para-spinal gross tumor should not be included in this structure.

6.6.4 Esophagus

The esophagus will be contoured using mediastinal windowing on CT to correspond to the mucosal, submucosa, and all muscular layers out to the fatty adventitia. The esophagus should be contoured 5 cm above the superior extend of the PTV and continued on every slice to 5 cm below the inferior extent of the PTV.

6.6.5 Small Intestine

Small intestine will be contoured if the PTV is within the range of T10-L5. The small intestines should be contoured as a conglomerate of all bowel loops within each CT cut starting at the first appearance of small intestine in the pelvis and extending superiorly up to the level of the sacral promontory within each cut.

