6.1.2 Dose Fractionation

Patients will be treated by two different dose fractionation schedules decided by a prior history of radiation to the treated area. Patients with no prior treatment will receive a single fraction of radiation. Each patient will have two target volumes of interest regardless of fractionation, a Planning Treatment Volume (PTV) and a Gross Tumor Volume (GTV) defined below. Minimum prescription dose for the single fraction treatment will be 14 Gy to at least 95% of the PTV and 20 Gy to at least 90% of the GTV. The plans overall maximum dose must occur within the GTV and be no greater than 25 Gy. For the single dose regimen, the spinal cord will receive no greater than 14 Gy to a point, 10 Gy to no more than 0.25 cc of spinal cord volume, and 7 Gy to no more than 0.5 cc of spinal cord volume. Patients with prior radiation treatment will be treated with 5 fractions of radiation. A minimum of 14 hours and a maximum of 7 days should separate each treatment. Minimum prescription dose for the five fraction treatment will be 2.8 Gy per fraction to at least 95% of the PTV for a total dose of 14 Gy and 4 Gy per fraction to at least 90% of the GTV for a total dose of 20 Gy. The plan's overall maximum dose must occur within the GTV and be no greater than 5 Gy per fraction for a total dose of 25 Gy. For the five fraction retreatment regimen, the spinal cord will receive no greater than 14 Gy (2.8 Gy per fraction) to a point, 10 Gy (2 Gy per fraction) to no more than 0.25 cc of spinal cord volume, and 7 Gy (1.4 Gy per fraction) to no more than 0.5 cc of spinal cord volume. Treatment dose will prescribed typically to the 70-90 percent isodose line for each fractionation scheme.

Structure	Dose	Required Volume	Minor Volume Variation	Major Volume Variation	Required Conformality index (CI)
PTV	≥14 Gy	$\geq$ 95%	90% - 95%	< 90%	1.3
F I V	≥ 12.6 Gy	$\geq$ 99%	95% - 99%	< 95%	
GTV	20 Gy	≥90%	85% - 90%	< 85%	

Total doses will be the same for the single fraction and five fraction treatments

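### Section 6.6.5 ends the small-intestine contour below every level that triggers it, so a literal reading can leave jejunum/ileum beside the target out of the single-fraction dose check

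*Combined protocol and SAP*

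**What the plan says.** Section 6.6.5 sets the trigger: "Small intestine will be contoured if the PTV is within the range of T10-L5". Its next sentence sets the extent. The bowel loops are drawn as one structure, beginning where small intestine first appears in the pelvis and "extending superiorly up to the level of the sacral promontory within each cut".

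Section 6.5.1 states what contours are for: "In order to verify each of these limits, the organs must be contoured such that appropriate dose volume histograms can be generated". It then points the reader to section 6.6: "Instruction for the contouring of these organs will follow below". On the status of the limits it says: "These are absolute limits, and dose that exceeds these limits by 5% will constitute a major protocol violation". The one-fraction table in 6.5.2 gives jejunum/ileum a volume limit of less than 5 cc at 9.8 Gy and a maximum point dose of 19 Gy.

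On target dose, 6.1.2 says: "Minimum prescription dose for the single fraction treatment will be 14 Gy to at least 95% of the PTV". It also caps the plan: "The plans overall maximum dose must occur within the GTV and be no greater than 25 Gy".

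Three other structures in 6.6 are located by reference to the target. The cord is drawn at least 2.5 cm above and below the PTV (6.6.1), and the cauda equina where it lies within 5 cm of it (6.6.2). For the esophagus, "The esophagus should be contoured 5 cm above the superior extend of the PTV", and likewise 5 cm below (6.6.4).

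**The concern.** The bowel that matters for a vertebral target is the bowel at the level of that target. The extent sentence in 6.6.5 leaves it out: the contour stops at the top of the sacrum, while the rule applies only to targets from T10 to L5. The instruction that 6.5.1 says will follow therefore cannot, for jejunum/ileum, deliver the verification that 6.5.1 demands.

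At stake is a safety check. A histogram built from pelvic bowel alone could show the 9.8 Gy volume limit as met, and no violation would be scored under 6.8.2, whatever dose the adjacent loops received. The primary endpoint and the two-stage designs are not touched.

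**Working it through.** The plan states no figure to reproduce. The check sets the sections side by side and adds simple dose arithmetic.

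**Inputs from the protocol**
- 6.6.5: trigger T10-L5; contour from the pelvis up to the sacral promontory.
- 6.5.2, jejunum/ileum: one fraction, less than 5 cc at 9.8 Gy and point maximum 19 Gy; five fractions, less than 5 cc at 19.5 Gy and point maximum 35 Gy.
- 6.1.2: PTV dose 14 Gy, GTV dose 20 Gy, plan maximum 25 Gy, with the same totals in both schedules.
- 6.4.3: prescription isodose volume divided by PTV volume below 1.3; tissue outside the PTV above 105% of prescription at most 15% of the PTV volume.
- 6.8.2: minor violation above a 2.5% excess, major above 5%.

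**Assumption:** PTV volumes of 10, 20, 40 and 60 cc. The documents give none.

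**1. Geometry.** The promontory is the upper front edge of S1, just below L5 (general anatomy). The defined contour therefore reaches none of the triggering levels. The gap is smallest at L5, and at T10 there may be little jejunum or ileum beside the target.

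**2. Limit against target dose, single fraction.** 9.8 / 14 = 70%. Minor violation: above 9.8 × 1.025 = 10.05 Gy. Major: above 9.8 × 1.05 = 10.29 Gy. The limit is well below the dose prescribed to the PTV, so bowel close to the target could exceed it.

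**3. Do the plan-quality rules cover the same dose range?** Conformality acts at the prescription isodose, 14 Gy. Spillage acts above 1.05 × 14 = 14.7 Gy. Neither acts between 9.8 and 14 Gy. If the 20 Gy GTV dose is read as the prescription, the thresholds become 20 and 21 Gy and the uncovered range widens.

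**4. What conformality allows at 14 Gy or more.** With 95% of the PTV covered, the outside volume is below (1.30 − 0.95) × PTV = 0.35 × PTV. With full coverage it is below 0.30 × PTV. This reaches 5 cc at 5 / 0.35 = 14.3 cc and 5 / 0.30 = 16.7 cc respectively. The spillage allowance, 0.15 × PTV, reaches 5 cc at 33.3 cc.

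| Assumed PTV (cc) | Outside tissue allowed by conformality (cc) | Allowed by spillage (cc) |
|---|---|---|
| 10 | 3.0–3.5 | 1.5 |
| 20 | 6–7 | 3 |
| 40 | 12–14 | 6 |
| 60 | 18–21 | 9 |

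These volumes are all tissue outside the PTV (muscle, vessels and other organs included), not bowel alone. They show that the rules do not guarantee the 5 cc limit; they do not estimate bowel dose. Near the 19 Gy point limit, the spillage rule restricts volume but does not cap a point.

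**5. Five fractions.** 19.5 / 14 = 139% of the PTV dose, and 19.5 Gy lies above the 14.7 Gy spillage threshold. The 35 Gy point limit cannot be reached under a 25 Gy plan maximum. The effect is small here. The larger question in this group is earlier bowel dose, which 6.5.2 leaves to clinical judgement.

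**The case against.** The strongest reply is that 6.5.1 already requires the missing contour, and in stronger terms: organs *must* be contoured to verify the limits, whereas 6.6.5 says how far the bowel *should* be drawn. Section 6.6 is also not a full atlas. Stomach, duodenum, colon, liver, great vessels and others have limits but no contouring instruction, so planners must apply 6.5.1 unaided for them anyway. Nor is tying contours to the PTV universal in 6.6: kidneys, heart and lungs are not handled that way.

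Much of this stands. The mandatory rule points to the safer reading, and a competent planner may well follow it. But doing so means departing from the only specific extent that the protocol gives. An incorrect instruction can mislead where a missing one would not, and the protocol provides for more than one institution, so practice could differ.

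Other safeguards exist. Jejunum/ileum carries the footnote against circumferential irradiation in both tables, and 6.5.1 encourages prudent planning whatever the limits. Both apply to bowel at the treated level, but neither is a numeric check at 9.8 Gy. Accreditation (5.3.1) can call for extra data and site visits, but it tests against protocol criteria and so does not by itself correct this text. The first radiotherapy quality review (6.9) follows complete data on the first 9 single-fraction cases.

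A reader might infer that bowel goes unprotected in this trial, or that patients will exceed the limit. The documents support neither. The safeguards above exist, and no bowel doses, bowel-to-target distances or counts of T10-L5 cases are given. The absence of a CTV-to-PTV margin (6.4.2) also reduces overlap with bowel.

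**Conclusion.** The point holds as a drafting conflict with a limited safety consequence. As written, 6.6.5 cannot provide the check that 6.5.1 requires for jejunum/ileum. A planner who follows it literally can report the single-fraction limit as met from a histogram that omits the adjacent bowel.

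The consequence is essentially confined to those of the 29 planned single-fraction patients who have a T10-L5 target; it is small for the 13 planned five-fraction patients. The conflict in the text is certain. The clinical effect depends on planners following 6.6.5 over 6.5.1 and on bowel lying close enough to the target to receive more than 9.8 Gy, neither of which the documents establish. The volumes in step 4 rest on assumed PTV sizes. The conclusion covers jejunum/ileum only: duodenum is not named in 6.6.5, and its gap is a missing instruction rather than a wrong one. The text should be corrected; nothing here calls the efficacy design into question.

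**What to change.** Replace the whole extent sentence in 6.6.5, both the pelvic start and the promontory stop. Changing only the upper bound would leave a competing lower one. Suggested text:

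*Jejunum/ileum loops should be contoured as one structure on every CT slice from a set distance below to the same distance above the PTV (for example 5 cm, as for the esophagus, to be confirmed by the study committee).*

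The 5 cm is borrowed from 6.6.4 and has no bowel-specific support in the documents, hence the confirmation. Optionally, add that duodenum within this range is contoured as a separate structure, because it has its own limits in 6.5.2.

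The cost is one or two sentences and some extra contouring time per T10-L5 case.

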#### 6.6.6 Kidneys

Kidneys will be contoured if the PTV is within the range of T10-L5. Each kidney should be contoured and evaluated separately. Kidney should be contoured on abdominal windows on CT.

6.6.7 Heart

The heart will be contoured along with the pericardial sac. The superior aspect (or base) for the purposes of contouring will begin at the level of the inferior aspect of the aortic arch (aorto-pulmonary window) and extend inferiorly to the apex of the heart.

6.6.8 Skin

The skin will constitute the external contour minus 5 mm. The skin within folds, especially in the gluteal folds as the skin surfaces make contact, will be contoured as a separate structure.

#### **6.7 Documentation Requirements**

6.7.1 In general, treatment interruptions should be avoided by preventative medical measures and nutritional, psychological, and emotional counseling. Treatment breaks, including indications, must be clearly documented on the treatment record.

#### 6.8 Compliance Criteria

#### 6.8.1 Accreditation Compliance

All criteria listed in Section 5 must be completed to the satisfaction of the study committee in order to be accredited. Upon completion of the criteria, a letter will be sent to institutions' PIs informing them of accreditation for the study. No institution will be allowed to enroll patients without accreditation.

- 6.8.2 Dosimetry Compliance Section 6 describes appropriate conduct for treatment planning dosimetry. The table in Section 6.5 lists dose volume limits for specific organs and structures. Exceeding these limits by more than 2.5% constitutes a minor protocol violation. Exceeding these limits by more than 5% constitutes a major protocol violation and should be strictly avoided.
- 6.8.3 Treatment Delivery Compliance Set-up films will be compared to digitally reconstructed radiographs from the same beam's eye view. Deviations of less than 0.3 cm will be considered compliant. Deviations from 0.3-0.5 cm will be considered minor protocol deviations. Deviations greater than those listed as minor will be considered major protocol deviations.
- 6.8.4 Target Coverage Compliance

As listed in sections 6.1.2 and 6.4.3, the protocol requires that 95% of the PTV volume be given the protocol dose while 99% of the PTV volume should get 90% of the prescribed dose. A minor violation would be issued for PTV prescription dose coverage of 90-95% while and a major violation for <90%. A minor violation will be issued if between 95-99% of the target volume receives 90% of the prescribed dose, while a major violation for <95% of the volume. In regard to the GTV coverage, a minor violation will be issued for coverage of 85-90% of the volume by the prescription dose, while a major violation for <85% of the volume.

#### 6.9 R.T. Quality Assurance Reviews

[name] will perform an RT Quality Assurance Review after complete data for the first 9 cases enrolled into the single fraction group and 6 patients enrolled into the four fraction group have been received at the University of Texas Southwestern. [name] will perform the next review after complete data for the next and subsequent 15 cases enrolled has been received at the University of Texas Southwestern. The final cases will be reviewed within 3 months after this study has reached the target accrual or as soon as complete data for all cases enrolled has been received, whichever occurs first.

#### 6.10 Radiation Adverse Events

6.10.1 Neurology

Monitored treatment related toxicity associated with neurology function will include myelitis, motor and sensory neuropathy, plexopathy, and pain. The consequences of neurology toxicity should all be graded according to the Common Terminology Criteria For Adverse Events (CTCAE).

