The initial complication rate of vertebroplasty in patients with metastatic disease is reported to be approximately 10%[23]. This is significantly higher that observed when the procedure is done for osteoporotic compression fractures (2-5%). This is likely secondary to increased bony destruction in the cancer patient. Reported complications include cement leakage into the spinal canal, neural foramina or paraspinous soft tissue. Notably, most cement leaks are asymptomatic and the long term complication rate is reported to be 1.7%. Cement leakage into the neural foramina can cause a painful radiculopathy which typically improves spontaneously in most patients. Extravasation into the spinal canal can cause spinal cord compression. In some instances surgery to decompress the neural structures was necessary. Extravasation into the epidural venous plexus or inferior vena cava can result in pulmonary embolism[26]. Increased back pain after the procedure has also been reported and is thought to be secondary to local irritation from the PMMA. This typically responds well to a short course of non-steroidal anti-inflammatory medications[25].

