#### 3.0 Patient Selection:

3.1 All patients must be willing and capable to provide informed consent to participate in the protocol.

- 3.2 Histologic confirmation of cancer will be required by biopsy, prior surgery, and re-biopsy at the discretion of the treating physician.
- 3.3 The patient's Zubrod performance status must be 0-2
- 3.4 Patients must be or have been ambulatory within a week prior to treatment.
- 3.5 Patients with instability of the spine requiring instrumentation as judged by a neurosurgeon are not eligible.
- 3.6 No planned systemic treatment is allowed within one week after treatment.
- 3.7 Patients must have localized spinal metastasis. This includes patients with a solitary lesion, a lesion that spans two contiguous levels, a lesion with a para-spinal component, and up to three separate single vertebral levels.
- 3.8 Patients with loss of normal vertebral height, due to for example compression fracture or other process, prior to treatment are not allowed. Patients with normal height and compression fracture are allowed.
- 3.9 Patients with prior fractionated radiation to the treated site are allowed. Their prior treatment plan with date, fractionation, dose and treatment fields must be obtained. There must be at least a three month interval elapsed from the prior radiation to the treated site and enrollment.
- 3.10 Patients must have had a visual analog scoring of pain  $\geq$ 4 at the planned treated site within 14 days of registration. Pain must be ongoing or require narcotic pain medicine to control.
- 3.11 Narcotic pain prescription and usage information must be available and documented.
- 3.12 Radiation sensitive histology such as lymphoma, myoloma, or plasmacytoma are not allowed.
- 3.13 Patients must be past their 18th birthday at time of registration.
- 3.14 Women of childbearing age must have documentation of a negative pregnancy test and agreed that they or their partner use an effective contraceptive method such as condom/diaphragm and spermacidal foam, non-stainless-steel intrauterine device, or prescription birth control pills.
- 3.15 Patients should not have a history of significant psychiatric illness.
- 3.16 Patients should not have severe, active co-morbidity that would preclude vertebroplasty or stereotactic radiotherapy, defined as follows:

3.16.1 Unstable angina and/or congestive heart failure requiring hospitalization within the last 6 months.

3.16.2 Transmural myocardial infarction within the last 6 months.

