3.16.3 Acute bacterial or fungal infection requiring intravenous antibiotics at the time of registration.

3.16.4 Hepatic insufficiency resulting in clinical jaundice and/or coagulation defects.

3.17 Laboratory entry criteria:

3.17.1 PT within normal limits or planned and feasible to be corrected to normal limits prior to vertebroplasy.

3.17.2 PTT within normal limits or planned and feasible to be corrected to normal limits prior to vertebroplasy.

3.17.3 Platelet count must be  $\geq$  50,000.

3.18 Patient with epidural, spinal nerve, and/or cord compression on MRI may be included.

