4.1 Required Evaluations/Management

4.1.1 History and physical exam to include: determination and description of pain from spine metastasis and full neurological exam, VAS for given painful area, BPI, FACT-G, and EQ-5D.

- 4.1.2 Zubrod performance status (Appendix III).
- 4.1.3 Imaging studies to include: complete spine MRI and plain radiographs of involved areas
- 4.1.4 Laboratory work to include: complete blood count with platelets and differential within 30 days or after last round of chemotherapy, Electrolytes, BUN and creatinine as appropriate for histology
- 4.2 Highly Recommended Evaluations/Management
  - 4.2.1 Dedicated spine CT if clinically indicated or radiographic correlation is needed to evaluate the vertebral body cortex and look for bone fragments within the spinal canal.

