#### 6.11 Serious Adverse Event Reporting

6.11.1 ERGO

Electronic Research Grant Organizer (ERGO) constitutes a mechanism for reporting serious adverse events to the UTSW IRB for reporting purposes.

Any adverse event equivalent to CTCAE V.3 grade 3, 4, or 5 or which precipitates hospitalization or prolongs an existing hospitalization must be reported regardless of designation (expected or unexpected) along with the attribution. This includes all deaths that occur within 30 days after the patient was discontinued from the study regardless of attribution AND any events that occur beyond 30 days and are considered probably related to treatment.

Participating sub-sites must file an SAE report (the CRF plus information describing the event, the grade, and the attribution) within 48 hours of the investigator's awareness of the occurrence of the event.

Attribution of an event can be categorized as:

- Not Related
- Possibly Related
- Likely Related

Adverse events (below grade 3) do not need to be submitted immediately. Rather, they should be documented in the Adverse Events CRF along with a brief description of the event, grade, and attribution).

All SAE reports should be made via FAX transmission to:

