## Appendix I

## **STUDY PARAMETER TABLE**

	PreTreatment		During Treatment			Follow-Up (months after therapy)				
	Within 30 days of study entry		After last treatment	1	3	6	Every 6 months for three years			
Confirmation of Pathology	Х									
History/physical	Х	Х	Х	Х	Х	Х	Х			
Performance Status	Х			Х	Х	Х	Х			
MRI spine*	$X^1$			X1	X1	X 	X 			
CT spine*	$X^1$			$X^1$	$X^1$	X 	X 			
BUN, creatinine, CBC w/ platelets, PT/PTT INR	Х									
Informed consent	Х									
Tumor response evaluation	Х			Х	Х	Х	Х			
VAS at treated Site	Х		Х	Х	Х	Х	Х			
Adverse event evaluation		Х	Х	Х	Х	Х	X			
QOL Studies	Х		Х	Х	Х	Х	X			
(BPI, Fact-G, EQ-5D) Vertebroplasty	X	X 	1	x	x	x	(12 months only)			

 $*X^1$ : Per physician's discretion  $X^2$  : within one month of start of radiation treatment.

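### Pain and neurological toxicity are graded by absolute CTCAE severity with no baseline grade, in patients who enter with pain and possibly nerve or cord compression; recording a baseline grade is a cheap improvement

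*Combined protocol and SAP*

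**What the plan says.** Section 6.10.1, under the heading for radiation adverse events, reads "Monitored treatment related toxicity associated with neurology function will include myelitis, motor and sensory neuropathy, plexopathy, and pain" and sends these terms to CTCAE for grading. Section 11.3.1 scores acute and late events from protocol radiation for severity on CTCAE version 3.0. Section 6.11.1 sets the reporting trigger: "Any adverse event equivalent to CTCAE V.3 grade 3, 4, or 5 or which precipitates hospitalization". Each report carries one of three attributions (not, possibly or likely related), with no criteria for choosing among them. Section 14.0 gives a monitoring committee access to patient information and asks it to scrutinise grading and attribution.

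On entry status, section 3.10 begins "Patients must have had a visual analog scoring of pain" and sets the threshold at 4 or more within 14 days of registration; the pain must be ongoing or need narcotics to control it. Section 3.18 adds: "Patient with epidural, spinal nerve, and/or cord compression on MRI may be included".

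On baseline data, section 4.1.1 requires "determination and description of pain from spine metastasis and full neurological exam", together with VAS, BPI, FACT-G and EQ-5D. In Appendix I, the row labelled "Adverse event evaluation" has no mark in the pretreatment column. No section records a CTCAE grade before treatment or defines an adverse event as new or worsened from baseline.

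**The concern.** The symptoms monitored as toxicity are the ones patients may bring to the trial. Pain is an entry requirement, and motor or sensory deficits are plausible at entry when nerve or cord compression is admitted. Harm from treatment is a change from that starting point, as the plan's own background on vertebroplasty recognises: "Increased back pain after the procedure has also been reported". An absolute grade does not measure change.

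Two errors become possible in the safety summary. Persisting disease pain may be listed beside treatment-caused pain at the same grade. Conversely, a deficit that moves from grade 1 to grade 2 after treatment looks the same, in a table of worst grades, as one that was grade 2 throughout; it also falls below the grade 3 reporting trigger. With no control arm, no background rate is available for comparison. What is at stake is the clarity of the safety description and of the committee's review. The efficacy conclusion is not at stake.

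**Working it through.** **1. The sections side by side**

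- Pain. At entry: VAS of at least 4 is required (3.10). Recorded before treatment: description, VAS and BPI (4.1.1). Graded afterwards: CTCAE (6.10.1, 11.3.1). Baseline CTCAE grade: none.
- Neuropathy and myelitis. At entry: nerve and cord compression allowed (3.18). Recorded before treatment: full neurological examination (4.1.1). Graded afterwards: CTCAE. Baseline CTCAE grade: none.
- Appendix I. The history/physical row has seven marks, the first in the pretreatment column, and the VAS row also has a pretreatment mark. The adverse event row has six marks, starting during treatment. The table layout is imperfect in the copy reviewed, but the contrast between rows is clear.

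The raw material for a comparison with baseline therefore exists. The instruction to make that comparison does not.

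**2. An example**

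A fall in VAS from 9 to 7 with no increase in narcotics is a partial response under 11.4.2.3. A score of 7 lies in the severe band (7-10) that section 1.5.2 gives for the BPI. The same patient can be a responder and still have severe pain by that description. The band belongs to the BPI; no section ties a VAS of 7 to a CTCAE grade.

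**3. Illustration of background pain, with no treatment-caused pain**

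Inputs from the plan: response rates of 0.50 and 0.80 with 29 patients (13.1); 0.35 and 0.75 with 13 patients (13.2).

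Assumed, because the plan gives no figures: entry VAS uniform on the seven values 4 to 10; non-responders change by 0 or -1 with equal probability; responders fall by a uniform amount from 2 up to their entry score.

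- Non-responders in the plan: 29 × 0.20 = 5.8 to 29 × 0.50 = 14.5; 13 × 0.25 = 3.25 to 13 × 0.65 = 8.45.
- P(VAS ≥ 7, non-responder) = ½ × 4/7 + ½ × 3/7 = 0.50.
- P(VAS ≥ 7, responder) = (1/8 + 2/9)/7 = 0.0496. Only entry scores of 9 and 10 contribute.
- Share still at 7 or more = (1 - p) × 0.50 + p × 0.0496.
- Single fraction: p = 0.80 gives 0.100 + 0.040 = 0.140 (4.1 of 29); p = 0.50 gives 0.250 + 0.025 = 0.275 (8.0 of 29).
- Five fractions: p = 0.75 gives 0.125 + 0.037 = 0.162 (2.1 of 13); p = 0.35 gives 0.325 + 0.017 = 0.342 (4.5 of 13).
- Entry scores weighted 7 down to 1 across 4 to 10: 7-15% and 8-19%. Weighted 1 up to 7: 21-40% and 24-49%.

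A second illustration works on the grade itself, again with assumed inputs. If 10-50% of the 42 patients had grade 3 pain at baseline and it persisted to a follow-up visit in 20-50% of them, the expected count is 42 × 0.10 × 0.20 = 0.8 to 42 × 0.50 × 0.50 = 10.5.

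**4. What is not affected**

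The primary endpoint uses VAS and narcotic requirement, not CTCAE. Both Simon designs reproduce by exact binomial calculation:

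- Single fraction: type I error 0.0477, power 0.9048, early termination 0.746, expected size 9 + 20 × 0.254 = 14.08.
- Five fractions: type I error 0.0431, power 0.9045, early termination 0.647, expected size 6 + 7 × 0.353 = 8.47.

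**The case against.** A reader might infer that entry symptoms and treatment harm cannot be separated at all. The documents do not support that. Section 4.1.1 requires a pain description, VAS, BPI and full neurological examination before treatment. VAS and neurological examinations continue for three years and BPI to 12 months. Sections 6.10.1 and 11.3.1 confine toxicity to treatment-related events and to events from protocol radiation, so an unchanged entry symptom is not toxicity on those words. The committee can open the patient's information. All of this stands. What it leaves open is the rule: nothing states how the baseline findings enter the grade, and attribution has no criteria.

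A reader might also take the percentages above as toxicity rates, or set them against the initial vertebroplasty complication rate of about 10% in section 1.3. Neither is supported. The cut at 7 is a BPI band, the entry distribution is assumed, and neuropathy and myelitis have no figure. The 10% is not a pain-toxicity rate; the complications listed with it are mainly cement leaks, most of them asymptomatic. The increase in back pain described there is likewise a vertebroplasty effect, whereas 6.10 covers radiation.

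Section 12.1 might be read as starting adverse event assessment only after the last treatment. It is a submission timeline for forms and does not show that; Appendix I marks evaluation during treatment.

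Finally, a baseline grade does not by itself distinguish tumour progression from radiation injury. That is correct, and attribution is still needed. The baseline grade gives attribution a documented starting point.

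**Conclusion.** The gap is real and modest. Pain, neuropathy and myelitis are graded by absolute CTCAE severity, no baseline grade is scheduled, and no section links the baseline VAS, BPI and neurological examination to adverse event grading. In an uncontrolled trial that leaves the separation of entry symptoms from harm to judgement case by case. Toxicity is not among the objectives in section 2.0 and section 13.3 plans no toxicity analysis, so the effect is confined to the safety description and the committee's review.

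The documents fix no size in CTCAE terms. The 14-27% and 16-34% shares, or 7-49% across the entry weightings tried, rest wholly on the stated assumptions. They show only that disease pain with no treatment contribution could be common at one month; how much of it would be reported as toxicity depends on attribution. Entry pain may also be controlled by narcotics, so pain on the treatment day can be lower than the qualifying score. This is a worthwhile, inexpensive improvement and not a flaw in the design.

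**What to change.** - In Appendix I, mark adverse event evaluation in the pretreatment column.
- Record a baseline CTCAE grade for the section 6.10 terms, at least neurology and pain, from the history, neurological examination and VAS that 4.1.1 already requires.
- In 6.10 and 11.3.1, state that both the worst grade and the increase over baseline will be reported per patient, with attribution, identifying events that are new or at least one grade worse.
- For pain, show the change in treated-site VAS together with the change in narcotic use, and keep new pain at other sites as an event. Counting only a rise in treated-site VAS would miss that new pain, and would miss worsening masked by more narcotics.
- Leave the expedited reporting in 6.11.1 unchanged.

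The cost is one calendar mark, a baseline column on the adverse event form and a sentence in each of two sections. No visit or test is added. The downside is slightly more form completion at entry.
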